#### **8.5. Replacement of individual subjects after withdrawal**

No replacement of individual subjects will take place after withdrawal.

#### **8.6. Follow-up of subjects withdrawn from treatment**

This is an observational cross-sectional study without any follow-up period.

#### **8.7. Premature termination of the study**

The study will be terminated prematurely if the nationwide quarantine is unexpectedly lifted within a week. In that case, the inclusion of participants will be stopped. Also, the study will be terminated if it is temporarily suspended for reasons of subjects' safety and the accredited METC gives a negative decision after assessing the reasons that led to the temporary suspension (see below).

## 9. SAFETY REPORTING

### 9.1. Temporary halt for reasons of subject safety

In accordance to section 10, subsection 4, of the WMO, the sponsor will suspend the study if there is sufficient ground that continuation of the study will jeopardise subject health or safety. The sponsor will notify the accredited METC without undue delay of a temporary halt including the reason for such an action. The study will be suspended pending a further positive decision by the accredited METC. The investigator will take care that all subjects are kept informed.

### 9.2. AEs, SAEs and SUSARs

#### 9.2.1. Adverse events (AEs)

Adverse events are defined as any undesirable experience occurring to a subject during the study, whether or not considered related to the study procedure. All adverse events reported spontaneously by the subject or observed by the investigator or his staff will be recorded.

#### 9.2.2. Serious adverse events (SAEs)

A serious adverse event is any untoward medical occurrence or effect that

- results in death;
- is life threatening (at the time of the event);
- requires hospitalisation or prolongation of existing inpatients' hospitalisation;
- results in persistent or significant disability or incapacity;
- is a congenital anomaly or birth defect; or
- any other important medical event that did not result in any of the outcomes listed above due to medical or surgical intervention but could have been based upon appropriate judgement by the investigator.

An elective hospital admission will not be considered as a serious adverse event.

The investigator will report all SAEs to the sponsor without undue delay after obtaining knowledge of the events.

The sponsor will report the SAEs through the web portal *ToetsingOnline* to the accredited METC that approved the protocol, within 7 days of first knowledge for SAEs that result in death or are life threatening followed by a period of maximum of 8 days to complete the initial preliminary report. All other SAEs will be reported within a

period of maximum 15 days after the sponsor has first knowledge of the serious adverse events.

### 9.2.3. Suspected unexpected serious adverse reactions (SUSARs)

NA.

### 9.3. Annual safety report

NA.

### 9.4. Follow-up of adverse events

All AEs will be followed until they have abated, or until a stable situation has been reached. Depending on the event, follow up may require additional tests or medical procedures as indicated, and/or referral to the general physician or a medical specialist. SAEs need to be reported till end of study within the Netherlands, as defined in the protocol.

### 9.5. [Data Safety Monitoring Board (DSMB) / Safety Committee]

NA. This is an observational cross-sectional study without any follow-up period.

## 10. STATISTICAL ANALYSIS

- Categorical data: gender, level of education, type of diabetes, medication use, type of blood glucose measurements (fingerprick or glucose sensor (FGM/CGM)) will be presented by percentage and standard deviation (SD).
- Continuous variables: age, BMI, weight, height, HbA1c will be presented using the mean and the standard deviation (SD). Derived parameters: BMI will be calculated from height (m) and weight (kg) using the formula  $(\text{weight (kg)} / (\text{height (m)})^2)$  and will be presented as continuous variable by mean and standard deviation (SD). Glucose variability will be calculated by the standard deviation of the glucose values from the continuous and flash glucose monitors obtained during the previous week in the quarantine period. This SD will be compared to the SD from the glucose values during the last non-quarantine week. Other glyceic measures include time spent in range 4.0-10.0 mmol/l, time spent in hypoglycaemia (<3.0, 3.0-3,5, and 3.5-3.9 mmol/l), time spent in hyperglycemia ( $\geq 10.0$  mmol/l)
- Missing data will be excluded from analyses.

- Data will be statistically analysed using STATA intercooled 16.0. HbA1c measurements and SD measurements prior to and after the quarantine period will be compared using a paired-sample t-test in case of normal distribution or Wilcoxon Signed Rank Test in case of abnormal distribution. Furthermore, differences in HbA1c and glucose variability between patients with type 1 and type 2 diabetes will be measured using independent T-tests. Differences in well-being, distress and self-management between patients with type 1 and type 2 diabetes will be analysed using independent T-tests. The association between glucose variability and parameters for distress, well-being and self-management will be analysed using multivariate regression analysis.

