The current study aims to assess the impact of self-quarantine on glycemetic control in patients with type 1 and type 2 diabetes. In addition, this study describes diabetes self-management, well-being and distress in Dutch patients with type 1 and type 2 diabetes, during a nationwide period of self-quarantine.

It is hypothesized that experiencing this period of nationwide quarantine influences glycemetic control and that patients reporting severe distress or low well-being experience more

problems in regard to diabetes self-management and maintaining glyceimic control than those without psychological distress or low well-being (13).

Research hypotheses:

H1: Experiencing self-quarantine impacts glyceimic control and glucose variability

H2: a) Experiencing high levels of distress is related to (poorer) glyceimic control

H2: b) Experiencing low levels of well-being is related to (poorer) glyceimic control

H3: a) Experiencing high levels of distress is related to suboptimal diabetes self-management

H3: b) Experiencing low levels of well-being is related to suboptimal diabetes self-management

H4: Experiencing self-quarantine impacts HbA1c, glucose variability, well-being, distress and self-management more in patients with type 1 than in patients with type 2 diabetes

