### Secondary Objective(s):

- To determine the effect of a period of nationwide self-quarantine on glucose variability assessed by the standard deviation (SD) of glucose values (glucose variability) in patients with type 1 and type 2 diabetes
- To assess the association between well-being and glycemc control during a period of nationwide self-quarantine. Well-being will be measured by the WHO-5.
- To assess the association between (diabetes) distress and glycemc control during a period of nationwide self-quarantine. (Diabetes) distress will be measured by 'Perceived Stress Scale'(PSS) and 'Problem Areas in Diabetes' (PAID).
- To assess the association between diabetes self-management and glycemc during a period of nationwide self-quarantine. Self-management behaviour will be measured by the 'Summary of Diabetes Self-Care Activities' (SDSCA) and 'Diabetes Self-Management Questionnaire-rev.' (DSMQ-R)
- To determine differences HbA1c, glucose variability, well-being, distress and self-management between patients with type 1 and type 2 diabetes

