### 3. STUDY DESIGN

This study is an observational, cross sectional study to assess the impact of self-quarantining on glyceimic control, diabetes self-management, distress and well-being. Patients with type 1 and type 2 diabetes mellitus currently in care at the diabetes outpatient clinic of the LUMC will be eligible to participate and will receive information about this study and an informed consent form. A few days later they will be contacted by phone to resolve any questions they may have and ask if the patient wants to participate in the study. If patients want to participate, they will sign the informed consent form and send it to the LUMC by mail. Once informed consent is provided, patients will be sent an envelope including a fingerprick device and a small tube. They will be asked to fill the tube with several drops of blood up to a mark on the tube and send the envelope back to the LUMC postage free. At the LUMC the HbA1c will be measured by the clinical chemistry lab. If the patients wears a continuous or FSL sensor, sensor data will be collected according to standard clinical practice. Furthermore, patients will receive a link by e-mail to a set of online questionnaires, containing the DSMQ-R, SDSCA, PSS, PAID and WHO-5, along with questions about level of education, medication use, employment, social situation and the impact of self-quarantine on daily routines. The HbA1c measurement and questionnaire will be performed at least 6 weeks after starting the quarantine period but still within a period of quarantine measures. Questionnaires will assess the extent and impact of the quarantine measures for each individual patient and assess the effect on glyceimic control, distress and well-being. Data on HbA1c measurements in the 12 months prior to the period of nationwide self-quarantine will be retrieved from the electronic health record of each patient, if available.

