#### **Stress: PSS**

*Perceived Stress Scale (PSS)*: The PSS is a 10 item scale designed to measure the degree to which situations' in one's life are appraised as stressful (17). Participants rate each item based on their recall of the past month and the degree to which they perceived

events as being stressful on a 5 point scale (never –almost never – sometimes – fairly often – very often). Four positively stated items are the reverse scored and then all scores are summed for an overall perceived stress score with higher score representing more perceived stress. A validated Dutch version is available.

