### **Diabetes Self-Management: SDSCA and DSMQ-R**

*The Summary of Diabetes Self-Care Activities (SDSCA)* .The SDSCA is a short questionnaire that covers basic aspects of diabetes self-care in regards to general diet, specific diet, exercise, blood-glucose testing, foot care, and smoking (20). The core questionnaire consists of 11 questions but it can be expanded and adapted to specific needs using the additional self-care items published with the original instrument. The core set of questions has been validated in Dutch.

*The Diabetes Self-Management Questionnaire-Revised (DSMQ-R)* questionnaire is a revision of the original Diabetes Self-Management Questionnaire and contains 20- items that asks the patient about their self-management based on the previous days (21). These items can be grouped into four subscales (glucose management, dietary control, physical activity, and physician contact) from which an overall sum score for 'diabetes self-management' can be calculated. All subscales as well as the overall sum score have shown to be highly correlated with levels of HbA1c. Additionally, the revised version has an additional 7-item subscale containing questions specific to insulin usage intended for patients using insulin.

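### H4 claims a larger quarantine impact in type 1 than in type 2 diabetes, but the planned between-type t-tests most naturally compare levels, and the five questionnaires have no pre-quarantine score

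*Protocol*

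**What the plan says.** H4 in Protocol section 1 states that quarantine "impacts HbA1c, glucose variability, well-being, distress and self-management more in patients with type 1 than in patients with type 2 diabetes". The matching secondary objective in section 2 is worded differently: "To determine differences HbA1c, glucose variability, well-being, distress and self-management between patients with type 1 and type 2 diabetes". It mentions neither change nor impact.

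Section 10 has three relevant sentences. The first is a before/after comparison: "HbA1c measurements and SD measurements prior to and after the quarantine period will be compared using a paired-sample t-test", with a Wilcoxon signed-rank test as the alternative. The second is the between-type comparison for the glycaemic outcomes: "differences in HbA1c and glucose variability between patients with type 1 and type 2 diabetes will be measured using independent T-tests". The third applies the same test to the questionnaires: "Differences in well-being, distress and self-management between patients with type 1 and type 2 diabetes will be analysed using independent T-tests". None of them names a comparison of change between types, a type-by-period interaction or a baseline adjustment. The Summary plans the HbA1c change within each patient group, but no contrast of those changes.

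A pre-quarantine value exists for HbA1c (sections 3, 8.3 and 10.1) and, in sensor users, for glucose SD (sections 10 and 10.2). WHO-5, PSS, PAID, SDSCA and DSMQ-R are given once (Summary, sections 8.3 and 11.2), and no earlier scores are retrieved.

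**The concern.** A claim that quarantine affects one type more than the other concerns a difference in before-to-quarantine change. A comparison of levels during quarantine answers another question. Type 1 and type 2 patients are not randomised groups and may have differed before quarantine. If levels are tested, a gap of long standing can be reported as support for H4 although both types changed equally, and an opposite gap can hide a real difference in change. Reporting the change within each type does not fill the hole: a significant change in one type and a non-significant change in the other does not show that the two changes differ.

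For the questionnaires the difficulty lies in the design. Without an earlier score, a conclusion that distress, well-being or self-management was hit harder in type 1 would rest on levels alone.

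**Working it through.** **Questionnaires (no arithmetic needed).** Section 3 places the measurement at least 6 weeks into quarantine. Where the protocol states a recall period, it does not reach back before quarantine. For the PSS, "Participants rate each item based on their recall of the past month"; the DSMQ-R "asks the patient about their self-management based on the previous days". No change on any of the five scales can therefore be computed, whatever the sample size. Section 3 also says that "Questionnaires will assess the extent and impact of the quarantine measures for each individual patient", but such items give no pre-quarantine score on the five instruments.

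**HbA1c: inputs.** Section 4.4 gives a difference of 4.0 mmol/mol, SD 11 mmol/mol, alpha 0.05, power 90% and 159 patients per type. It does not say whether 11 is the SD of levels or of change. I take it as the SD of levels at both times. The prior gap between types (2, 4 or 6 mmol/mol) and the pre/post correlation r (0.5 or 0.8) are assumptions, since the protocol gives neither.

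**The plan's own figure.** The two-sided two-sample formula gives 2 × (11 × (1.960 + 1.282) / 4)² = 158.9, so 159 per type. Invitations: 159 / (0.35 × 0.80) = 567.9, so 568 per type and 1136 in all. These figures reproduce and are not in dispute here.

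**Formulas.** Standard error of a level difference: 11 × √(2/159) = 1.23. SD of change: 11 × √(2(1 − r)), which is 11.0 at r = 0.5 and 6.96 at r = 0.8. Rejection probabilities use the noncentral t distribution, two-sided 0.05. The change-score results under equal change and all baseline-adjusted results come from simulation, 20,000 runs per cell.

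**Two ways in which there may be no differential impact.** (A) Both types change by the same amount. (B) The quarantine value depends on the prior value in the same way in both types (post = r × pre + error), with no type effect. Under B the expected level difference is r × gap and the expected difference in change is −(1 − r) × gap.

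| Rejection probability, gap 2 / 4 / 6 | r = 0.5 | r = 0.8 |
|---|---|---|
| A: level test | 0.37 / 0.90 / 0.998 | 0.37 / 0.90 / 0.998 |
| A: change-score test | about 0.05 | about 0.05 |
| A: baseline-adjusted regression | 0.15 / 0.45 / 0.77 | 0.08 / 0.19 / 0.35 |
| B: level test | 0.13 / 0.37 / 0.68 | 0.25 / 0.73 / 0.97 |
| B: change-score test | 0.13 / 0.37 / 0.68 | 0.08 / 0.18 / 0.34 |
| B: baseline-adjusted regression | about 0.05 | about 0.05 |

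**Masking.** If the true difference in change is 4.0 and the prior gap is 4 in the opposite direction, the level difference is 4 − 4 = 0 and the level test rejects with probability 0.05. With an opposite prior gap of 2 the level difference is 2 and it rejects with probability 0.37. The change-score test has power 0.90 at r = 0.5 and 0.999 at r = 0.8, with 95% CI half-widths of 2.43 and 1.54 mmol/mol. Lower correlations cost power: by the normal approximation it is 0.78 at r = 0.3 and 0.63 at r = 0.

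No figure is given for glucose SD, because the number of sensor users is not stated.

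**The case against.** The best counter-argument is that the glycaemic sentence in section 10 directly follows the before/after comparison of the same two variables, while the questionnaires get a sentence of their own. That layout fits an intended contrast of changes, and the exact variable entered in a secondary t-test could be settled in an SAP. This reading is possible. But the objective and the adjacent questionnaire sentence use the same construction where only levels can be meant, so the text does not fix which analysis is planned.

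It can also be said that the test does answer the objective in section 2, that section 1 describes the questionnaire domains partly in descriptive terms, and that the self-reported items in section 3 are also meant to capture effects on distress and well-being. All of this is accurate. None of it supplies a prior score on the five scales, and H4 still claims differential impact on them.

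A further possibility is the section 10.2 regression of HbA1c, which includes type of diabetes and previous HbA1c. It also conditions on WHO-5, PSS and PAID, domains that H4 says are themselves affected, and it was written for another question.

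Finally, the change score is not assumption-free. Under model B with r = 0.5 it rejects exactly as often as the level test. That stands, and it is why a baseline-adjusted result belongs beside it. In no scenario shown is the level test the better answer to H4.

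**Conclusion.** The concern holds and should be fixed. The questionnaire part of H4 cannot be tested under any reading of section 10. The HbA1c and glucose-SD part is worded so that the most natural analysis answers a different question from the hypothesis.

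The size for HbA1c applies only if levels are tested, and it depends on the assumed prior gap, the assumed correlation and on reading SD 11 as the SD of levels. Within those assumptions the error can go either way: near-certain false support for H4 at a prior gap of 6 with equal change, or no more than chance detection of a true 4.0 difference in change. Confidence is medium, because the glycaemic half turns on how one sentence is read. H4 is secondary, and the primary paired HbA1c comparison is not touched.

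**What to change.** - In section 10, state that H4 is tested for HbA1c and, in sensor users, for glucose SD by an independent comparison of within-patient change (quarantine minus pre-quarantine) between type 1 and type 2. This is equivalent to a type-by-period interaction. Report the difference in change with its 95% CI.
- Add a model adjusted for the pre-quarantine value as a sensitivity analysis if wanted, noting that it answers a different question when the types differ at baseline. Do not let the section 10.2 regression stand in for the H4 test.
- For the five questionnaires, restate H4 as a cross-sectional difference between types during quarantine. The self-reported impact items may be compared between types descriptively.

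The cost is two or three sentences and a narrower H4, with no data collection beyond what is planned. The study gives up a differential-impact claim from the questionnaire scores. The glucose-SD comparison is limited to sensor users, whose number is not stated. Section 3 retrieves prior HbA1c only where it exists, so fewer than 159 patients per type may have a computable change. The change-score and baseline-adjusted results may disagree if the types differed before quarantine.

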### 10.1. Primary study parameter(s)

#### **HbA1c**

HbA1c will be assessed in whole blood obtained by a fingerprick. The HbA1c will be compared to the last HbA1c in the non-quarantine period.

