## SUMMARY

**Rationale:** Diabetes mellitus is a chronic disease characterized by the inability of the body to maintain normoglycemia. Treatment of diabetes relies mostly on diabetes self-management, requiring a large investment of time and energy on a daily basis. Psychological wellbeing, behavioral patterns and social context have shown to play a major role in diabetes-self-management and glycemetic control. Self-quarantining may impact glycemetic control by influencing daily routines, self-measurement behavior, therapy adherence, physical activity and eating behaviors. A period of nationwide self-quarantine, such as during the outbreak of COVID-19 in the Netherlands, therefore may have a large effect on glycemetic control in patients with diabetes.

**Objective:** We aim to assess the impact of long-term self-quarantine on glycemetic control, diabetes self-management and distress in patients with type 1 diabetes mellitus (T1DM) and type 2 diabetes mellitus (T2DM).

**Study design:** This is an observational cross sectional study in Dutch patients with diabetes mellitus in tertiary care after self-quarantine for at least 6 weeks as result of the COVID-19 pandemic. Patients treated at the diabetes outpatient clinic of the Leiden University Medical Center (LUMC) will be approached for potential study participation. Measurements will be performed during the quarantine period or as soon as possible after. Patients will be asked to perform a fingerprick for HbA1c measurement once, which they can send back to the LUMC by mail. In addition, data from continuous glucose monitoring (CGM) or flash glucose monitoring (FGM) devices will be collected according to standard clinical practice. Furthermore, patients will be asked to fill out an online questionnaire once on diabetes self-management behaviour, well-being and distress, along with questions about health status, level of education, medication use, employment, social situation and the impact of self-quarantine on daily routines.

Data on demographics, type of diabetes, weight, BMI and HbA1c prior to the COVID-19 outbreak will be derived from the electronic health dossier of the patient. The most recent HbA1c will be used for data analysis.

**Study population:** Patients with T1DM and T2DM that are currently in care at the outpatient diabetes clinic of the LUMC are eligible for participation.

**Intervention (if applicable):** NA

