### 4.4. Sample size calculation

Patients with type 1 and type 2 diabetes mellitus are eligible for participation. HbA1c is the primary outcome parameter. Blood for HbA1c will be collected at home by a fingerprick and send to the LUMC. This is a method to obtain insight in glycemc control that many patients perform, and prefer, in clinical practice as it saves them a visit to the hospital. The clinical laboratory in the LUMC is set up to analyse these samples. But this method, which is appropriate in the context of social distancing and limiting hospital visits during this COVID-19 outbreak, also has some consequences regarding the number of patients that need to be approached. From clinical practice we know that not all patients carry out the blood sampling in an appropriate way, despite clear instructions. Also the duration in the postal service renders some samples not suitable for analysis. In this COVID-19 period the postal service

may take longer than normal. Based on our experience from clinical practice and the current COVID-19 situation we estimate that 20% of samples cannot be analysed for HbA1c. The aim is to detect a difference in HbA1c of 4.0 mmol/mol (standard deviation 11 mmol/mol) in comparison to the HbA1c prior to the period of quarantine, which is considered to be clinically relevant in our population of patients with often well regulated diabetes. For an alpha error of 0.05 and a power of 90%, the minimum sample needed is 159 patients per patient group (type 1 and type 2 diabetes). Taking in consideration an estimated response rate of 35% and an estimated proportion of 20% of HbA1c missing measurements as a result of logistical, practical or technical problems, 568 patients per patient group (type 1 and type 2 diabetes) will be invited to participate. This is a total of 1136 patients. The numbers of participants mentioned above are much higher than the number that is minimally needed (15 per variable) to calculate the hierarchical regression analyses (see statistical analyses) on secondary outcomes.

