### 8.3. Study procedures

Eligible patients from the diabetes outpatient clinic will be sent a letter with study information and informed consent forms. Within several days after receiving the letter, patients will be contacted by phone and will be invited to participate in the study as well as given the opportunity to ask questions. If patients are willing to participate they will be asked to sign the informed consent form and send it back to the LUMC by mail. Once informed consent is provided, patients will be sent a HbA1c fingerprick measurement envelope. They will be asked to fill the tube with several drops of blood up to a mark on the tube and send the envelope back to the LUMC postage free. At the LUMC the HbA1c will be measured by the clinical chemistry lab.

If patients are using a continuous or flash glucose monitoring device data of the most recent 3 months will be collected according to standard clinical practice.

Additionally, patients will receive a link in their e-mail to a set of online questionnaires, containing the DSMQ-R, SDSCA, PSS, PAID and WHO-5, along with questions about level of education, medication use, social situation, employment, impact of self-

quarantine on daily routines, and health status.

The HbA1c measurement and questionnaire will be performed once two months after the start of the nationwide quarantine phase as a result of the COVID-19 outbreak.

Data on HbA1c measurements in the 6 months prior to the period of nationwide self-quarantine will be retrieved from the electronic health record of each patient.

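### The primary before-and-after HbA1c comparison neither restricts nor records how the earlier value was sampled, so a sampling-method offset cannot be told apart from a quarantine effect

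*Protocol*

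**What the plan says.** The quarantine measurement has one method throughout. Protocol section 4.4 states: "Blood for HbA1c will be collected at home by a fingerprick and send to the LUMC." Sections 3, 8.3 and 11.2 describe the same procedure.

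Section 10.1 defines the comparison: "HbA1c will be assessed in whole blood obtained by a fingerprick. The HbA1c will be compared to the last HbA1c in the non-quarantine period." The Summary adds: "The most recent HbA1c will be used for data analysis." The source is the electronic health record, with two different look-back windows. Section 3 has "Data on HbA1c measurements in the 12 months prior to the period of nationwide self-quarantine will be retrieved from the electronic health record of each" …, whereas section 8.3 has "Data on HbA1c measurements in the 6 months prior to the period of nationwide self-quarantine will be retrieved from the electronic health record of each" …. That conflict needs reconciling but is a separate matter. Neither section says how the earlier sample was taken or which laboratory analysed it.

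Section 4.4 presents mailed fingerprick sampling as something many patients already do and like in routine care because it spares them a hospital visit. It also concedes that "not all patients carry out the blood sampling in an appropriate way, despite clear instructions", and continues: "Also the duration in the postal service renders some samples not suitable for analysis." It expects post to be slower during the pandemic. Its only response is to allow for 20% of samples that cannot be analysed.

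Section 10 plans a paired t-test, or a Wilcoxon signed rank test if the data are not normal. Neither has a term for sampling method. There is no concurrent comparison group.

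**The concern.** A paired test estimates the mean of the later value minus the earlier one. If the sampling method also changes between the two, that mean is the true change plus the average method offset. Nothing in the planned analysis separates them.

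Section 4.4 implies that some patients have their HbA1c taken at a hospital visit instead of by post. For those with a clinic-drawn earlier value, the switch to mailed sampling coincides with the switch from before to during quarantine. Slower post could also make two mailed samples from one patient differ in transit time.

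The primary objective is at stake. An offset would not average out with more patients. A larger sample makes a small offset more likely to reach significance.

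**Working it through.** **The plan's own figures (section 4.4).** Inputs: difference 4.0 mmol/mol, SD 11 mmol/mol, alpha 0.05, power 90%.

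- Two independent groups, two-sided: n = 2 × [11 × (1.960 + 1.282) / 4]² = 158.9, rounded up to 159 per diabetes type. This reproduces the stated number.
- Invitations: 159 / (0.35 × 0.80) = 567.9, rounded up to 568. This also reproduces.

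Section 4.4 does not say whether 11 is the SD of single values or of paired changes. I take 11 as the SD of change. That also follows from an SD of 11 at each time with a within-patient correlation of 0.5.

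**Precision per diabetes type.** SE = 11 / √159 = 0.872 mmol/mol. A mean change is significant beyond about 1.975 × 0.872 = 1.72 mmol/mol, which is less than half the 4.0 target.

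**Effect of an offset when the true change is zero.** Let b be the offset in pairs whose methods differ and s the share of such pairs. The mean paired difference is then s × b, and the test statistic is centred on s × b / 0.872. Rejection probabilities come from the noncentral t distribution with 158 degrees of freedom, two-sided 5%. The values of b and s are assumptions, because the protocol gives neither.

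| Offset b (mmol/mol) | Half the pairs differ: net offset | False positives | All pairs differ: net offset | False positives |
|---|---|---|---|---|
| 1 | 0.5 | 8.8% | 1 | 20.7% |
| 2 | 1.0 | 20.7% | 2 | 62.5% |
| 3 | 1.5 | 40.1% | 3 | 92.8% |

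If only a quarter of pairs differ, offsets of 1 and 2 give 5.9% and 8.8%.

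**Sensitivity to the SD of change.** SD of change = 11 × √[2 × (1 − r)]. With correlation r = 0.7 this is 8.5, and net offsets of 1 and 2 give 31% and 84%. With r = 0.8 it is 7.0, and they give 44% and 95%.

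**Masking.** With a true change of +4 and an SD of change of 11, the probability of a significant result is 99.5% with no offset, 92.8% with a net offset of −1, and 62.5% with a net offset of −2. The first figure exceeds 90% because 159 comes from a two-sample formula while the test is paired.

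**The case against.** The strongest reply is that the protocol shows no offset. The sampling and postal problems in section 4.4 are described as samples lost, and section 10 excludes missing data. No section says that an analysable mailed sample reads higher or lower than a clinic-drawn one. The method is in routine use and the hospital laboratory is set up for it. If many patients already use it, many pairs may match. All of this stands. It makes the concern conditional, and it is why the half-of-pairs column deserves as much weight as the all-pairs column.

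Four stronger readings are tempting but unsupported:

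- A reader might infer that incorrect sampling is common. Section 4.4 says only that not every patient samples properly, and gives no separate frequency for it.
- A reader might take the mixture of methods in the record as established. It is a natural inference from section 4.4, which gives no share.
- A reader might think that any HbA1c in the record will serve. The comparator is the last value before quarantine, from a look-back window. Only its sampling method and laboratory are left open.
- A reader might conclude that a method offset could produce the 4.0 mmol/mol change by itself. Net offsets of 1 or 2 can produce significance, but the expected estimate would be only 1 or 2. An estimate near 4.0 with no true change would need a net offset near 4.0, and nothing supports one.

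It may also be said that a sensitivity analysis belongs in a statistical analysis plan, which is not at hand. That is fair for the analysis detail. But the comparator and the data to be retrieved are set out in the protocol, and a later plan cannot stratify on a field that nobody collected.

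**Conclusion.** The concern holds as an uncontrolled risk of bias in the primary comparison. The protocol uses one sampling method for the later value, leaves the method of the earlier value open, and plans a test that cannot separate a method offset from a true change. It does not show that an offset exists, nor its size or direction.

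On the stated assumptions, offsets of 1 to 2 mmol/mol would raise the 5% error rate to about 9% to 21% with half the pairs affected, and to about 21% to 63% with all affected. An offset in the other direction could partly hide a true change. These figures rest on assumed offsets, assumed shares and an SD of change of 11. The error rates would be higher if within-patient correlation exceeds 0.5, and lower if fewer pairs differ in method. This is a worthwhile, inexpensive improvement, not a flaw that invalidates the design.

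**What to change.** In section 8.3, when the earlier HbA1c is retrieved, also extract how it was sampled (mailed fingerprick or clinic-drawn) and which laboratory analysed it. Log the sampling date and the receipt date of each study tube.

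In section 10.1, keep the analysis of all pairs as primary. Add a pre-specified sensitivity analysis that reports the paired change separately for same-method and different-method pairs, and that examines the change against days in transit. If the two sets disagree, say in the report that the primary result may reflect the change of sampling method.

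Do not make the primary conclusion depend on the same-method pairs. They are patients who had already chosen mailed sampling, and their number is unknown. If, for illustration, 40 of 159 pairs matched, the SE would be 11 / √40 = 1.74 and power for 4.0 mmol/mol about 63% by normal approximation.

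The cost is a few extra data fields and one additional analysis, provided that the record and the laboratory system hold these items. No extra patients or samples are needed. The drawback is that the same-method subset is smaller, less precise and self-selected, so it can inform interpretation but not decide it.
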